6.4 IMP administration

XR-Bup will be administered by subcutaneous injection into abdominal adipose tissue by the site investigator, medical practitioner, nurse, or nurse practitioner who have received training in the procedure and are delegated to perform this task. The drug will be prescribed for administration following local hospital requirements.

The specific area for administration is below the waist line and above the hip bone (specifically, in the region where the body curves at the side to about 2 inches from the middle of the abdomen i.e. between the transpyloric and trans tubercular planes), selecting a clear needle insertion point with adequate amounts of subcutaneous tissue that does not have excessive pigment, nodules, lesions, or hair or areas with brawny or fibrous subcutaneous tissue or locations that could be rubbed or compressed (i.e. with a belt or clothing waistband).

To avoid irritation, the injection site will be recorded and rotated across four different injection points for subsequent doses (with the patient's head pointing north), these will be, from the patient's perspective:

(1) right upper (RU); (2) left upper (LU); (3) left lower (LL) and (4) right lower (RL).

A cold press can be administered for up to 10 seconds prior to the injection.

6.5 IMP risks

The Reference Safety Information (RSI) for all information pertaining to IMP risk for the XR-Bup will be set out in the manufacturer's Investigators Brochure (IB). The SmPC will be the reference document for Bup/Met.

Adverse reactions (commonly associated in 5% or more of patients) receiving XR-Bup are: (a) constipation; (b) nausea; (c) vomiting; (d) headache; (e) fatigue; (f) increased hepatic enzymes; (g) injection site pain; (h) injection site pruritis.

Drug-drug interactions potentially relevant to the IMP (with Bup and XR-Bup) are as follows:

Drug Class	Drug(s) within Class	Clinical effect and suggested management
Benzodiazepines and Other Central Nervous System (CNS) Depressants	Alcohol, non-benzodiazepine sedatives/hypnotics, anxiolytics, tranquilizers, muscle relaxants, general anaesthetics, antipsychotics, and other opioids	
 - Increases the risk of respiratory depression, profound sedation, coma, and death. - Use of these substances should be stabilised during treatment with Bup products. Patients should be advised of the danger of concomitant use of sedatives while participating in the trial.
CYP3A4 inhibitors:	Macrolide antibiotics (e.g. erythromycin) Azole-antifungal agents (e.g. ketoconazole) Protease inhibitors (e.g. ritonavir)	
 - Effects of CYP3A4 inhibitors on Bup exposure in participants treated with XR-Bup have not been studied with Bup, however, such interactions have been established. - In the presence of CYP3A4 inhibitors, monitor for signs and symptoms of Bup toxicity or overdose. - Monitor for Bup withdrawal if the concomitant medication is discontinued after the patient is stable on. - The dose of either Bup or the CYP3A4 inhibitor may need to be adjusted accordingly.
CYP3A4 Inducers	Rifampin Carbamazepine Phenytoin	
 - Effects of CYP3A4 inducers on Bup exposure in participants treated with XR-Bup have not been studied, however, CYP3A4 inducers may induce its metabolism and lead to decrease in Bup plasma concentrations. - Monitor for signs and symptoms of Bup toxicity or overdose, if the CYP3A4 inducers is discontinued after the patient is stable on XR-Bup. The dose of either Bup or the CYP3A4 inducer may need to be adjusted accordingly.
Antiretrovirals: Non-nucleoside reverse transcriptase inhibitors (NNRTIs)	Efavirenz, nevirapine, etravirine, delavirdine	
 - Significant pharmacokinetic interactions between NNRTIs and Bup have been shown, but these pharmacokinetic interactions did not result in any significant pharmacodynamic effects. - Monitor for increase or decrease in therapeutic effects of NNRTIs.

Antiretrovirals: Protease inhibitors (PIs)	Atazanavir, ritonavir	
 - Treatment with atazanavir or atazanavir/ritonavir may result in elevated levels of Bup (and the metabolite nor-Bup). - If atazanavir +/- ritonavir is initiated once the patient is stable on XR-Bup, monitor for signs and symptoms of over-medication with Bup. If necessary, reduce XR-Bup dose from 300 to 100mg, or discontinue XR-Bup and treat with Bup to enable rapid dose adjustments.
Selective serotonin reuptake inhibitors (SSRIs) Serotonin and norepinephrine reuptake inhibitors (SNRIs) Tricyclic antidepressants (TCAs) Triptans 5-HT3 receptor antagonists Drugs that affect the serotonin neurotransmitter system inhibitors Monoamine oxidase (MAO)	e.g. mirtazapine, trazodone, tramadol e.g. linezolid and intravenous methylene blue	
 - May result in serotonin syndrome in high doses (e.g. overdose). Monitor for signs and symptoms of serotonin syndrome, particularly during treatment initiation, and during dose adjustment of the serotonergic drug.
Monoamine Oxidase Inhibitors (MAOIs)	e.g. Phenelzine, tranylcypromine, linezolid	
 - MAOI interactions with opioids may manifest as serotonin syndrome or opioid toxicity (e.g., respiratory depression, coma). - It is recommended that patients receiving Bup and MAOI should be closely monitored.
Diuretics		
 - May reduce the efficacy of diuretics by inducing the release of antidiuretic hormone. - Intervention: Monitor patients for signs of diminished diuresis and/or effects on blood pressure and increase the dosage of the diuretic as needed.
Anticholinergic Drugs		
 - May increase the risk of urinary retention and/or severe constipation, which may lead to paralytic ileus. - Monitor for signs of urinary retention or reduced gastric motility.
Opioid antagonists	Naltrexone, naloxone	
 - Opioid antagonists should generally not be used outside of emergency situations in patients in opioid agonist treatment, including XR-Bup. - Naloxone may be administered in response to an opioid overdose.

Opioid analgesics	Opioids	
 - Bup may reduce the effects of opioid analgesics through receptor blockade. Patients requiring analgesia should include non-opioid approaches (e.g. NSAIDs, ketamine). Opioids may be used with caution, but as higher doses may be required for analgesic effect, there may be a higher potential for toxicity with opioid administration, requiring close monitoring of opioid effects.
-------------------	---------	--

6.6 Treatment discontinuation

A participant is discontinued from the study medications for any of the following reasons:

- Participant safety reasons, including adverse events (AEs) or significant concomitant illness, injury, or urgent surgeries/procedures that would, in the opinion of the Investigator, compromise treatment safety or deterioration in the patient's clinical condition.
- Participant request to discontinue study intervention. A participant is free to withdraw from study intervention at any time for any reason (they do not need to state a reason). Their participation is to be terminated upon his/her request, and the reason(s) for discontinuation appropriately documented.
- At the request of the Sponsor, regulatory agency, or Ethics Committee.
- Pregnancy. If not terminating, participant to discuss with clinician and continue with oral medication or withdraw following usual practice. Participants receiving IMP will not receive further injections and will receive oral medication or withdrawal according to usual practice.
- Administrative discharge due to non-adherence with site policies (e.g. violence towards other clients or staff).

In the event of an emergency, or if clinically indicated, a decision to surgically remove depot (up to 14 days from injection) may be made by the CI or PI, following discussion with the participant. An appropriately skilled medical practitioner may perform the surgical procedure, as follows:

1. Palpate the depot and surrounding area to confirm location.
2. Cleanse the area with an antiseptic solution.
3. Infiltration the area with local anaesthesia and wait for it to take effect.
4. Cover the area with sterile drape.
5. Incise the skin up to the subcutaneous tissues using a scalpel.
6. Using blunt and sharp dissection, identify the plane between the depot and surrounding subcutaneous tissues. Once the plane is identified, separate the superficial 25% of the circumference of the depot with blunt dissection.
7. Gently lift the incised ellipse of skin and depot with forceps.
8. Once the depot is removed, ensure haemostasis, and close the skin with non-absorbable sutures.

Removal of the depot is to be recorded as an Important Medical Event (IME).

6.7 Drug accountability

6.7.1 XR-Bup

XR-Bup will be distributed to each site following the final QP release, and once all regulatory and local approvals are in place.

The pharmacy clinical trials team must maintain accurate accountability records for XR-Bup, including, but not limited to, the number of kits received, the number of kits dispensed to which patient, batch number, expiry date, and the date of the transaction, in addition to the quantity of unused investigational product and empty packaging returned to pharmacy for each patient. Trial specific prescriptions must be filed in the pharmacy trial file for audit purposes.

Sites must use a transfer log to record the transfer of:

- Dispensed XR-Bup from pharmacy to clinics
- Return of unused syringes and empty packaging from clinics back to pharmacy

The research team (clinic staff) must maintain accurate accountability records for XR-Bup, including, but not limited to, the number of kits received and administered for each individual patient and the date of the transaction, in addition to the number of unused kits returned to pharmacy. Administration records in clinics will be retained and monitored by the KHP-CTO during monitoring visits to ensure appropriate handling and storage of the IMP.

Unused XR-Bup and empty packaging (post dose) must be returned to pharmacy by the research team for reconciliation on the accountability log. The returns will be verified by the CRA prior to disposal at site. Destruction of XR-Bup must follow the site IMP destruction SOP and local hospital Controlled Drugs waste management procedure. After the KHP-CTO monitoring of IMP accountability is complete, destruction will occur following CI authorisation.

The King's Clinical Trials Unit (KCTU) clinical trials Pharmacist will track XR-Bup trial supplies at investigational sites and at Sharp Clinical Services, UK. The pharmacist will generate orders of IMP for delivery to sites and liaise with Indivior for the shipment of additional stock from the USA.

6.7.2 Met and Bup

Site staff will make a copy of the script record for the FP10 written for the trial and file in the relevant patients notes. Accountability records are not required for the active comparator arm (oral Met or Bup). Research teams will check medication compliance at clinic visits through questioning and clinical assessments. Adherence to oral medication – dispensed by community retail pharmacies – will be monitored as usual in the NHS by the retail pharmacy and the local clinic, such that if the patient does not attend to receive or collect three consecutive scheduled Met or Bup doses, this will trigger the pharmacy to inform the clinic. This event will be recorded in the patient's notes and should the patient present/contact the clinic requiring further Met or Bup, dosing will be re-started following the clinic's medication screening and induction protocol.

6.8 Supply, transport and storage of IMP

The Investigational Product Handling Manual gives detailed guidance on supply, transport and storage of IMP.

6.8.1 XR-Bup (Sublocade®)

XR-Bup must be stored in a locked fridge, maintaining a temperature between 2°C to 8°C. Appropriate storage conditions (for pharmacy and clinic fridges) must be ensured by completion of temperature monitoring logs.

Commercial USA licenced stock (Sublocade®) will be manufactured under contract to Indivior by Albany Molecular Research Inc. (AMRI), Burlington, MA. The stock will be imported into the UK. Labelling with an annex 13 compliant label, final QP release and distribution to UK sites has been contracted to Sharp Clinical Services, UK.

XR-Bup will be dispensed by the site pharmacy against a valid, sponsor approved clinical trial prescription. The dispensed XR-Bup will be transported to clinic, for the purpose of administration, using an appropriate transit method to maintain the cold-chain. The IMP transfer must be recorded on approved documentation to provide a full audit trail. Refer to section 6.6 of the protocol and the Investigational Product Handling Manual for further information.

On arrival at clinic, the dispensed XR-Bup will be checked and documented as received before being placed in a locked, temperature controlled and monitored pharmaceutical refrigerator.

Unused XR-Bup syringes and empty packaging will be returned to pharmacy for reconciliation prior to verification by the CRA. The sponsor must provide written permission for disposal prior to the product and empty packaging being destroyed at site. Participant compliance will be measured through medication dispensing records, attendance records and administration records.

After each participant's last visit, patients will transition to Met/Bup as appropriate according to local practice.

6.8.2 Active Comparators (Bup/Met)

Bup (including Bup-NX and Esp) and Met will be stored at community pharmacies in accordance with their SmPC's. Temperature monitoring records are not required for these products.

6.9 Concomitant Medication

Each participant's use of concomitant medications will be recorded continuously but reviewed at week 4, 12 and 24. The Investigator will record all medication used by the participant. This record will include the name of the medication, the dose, dates when drug was started and stopped.

7. Tailored Psychosocial Intervention

Convergent lines of epidemiologic and clinical research point to several behavioural factors which moderate Met/Bup effectiveness [10]. Addiction severity is moderator [11,12,13], and taking illicit drugs by injection correlates with higher levels of dependence and a likelihood of non-response [14]. Concurrent cocaine use and dependence is also common among the OUD population in the UK, and these patients tend to have poorer engagement with the clinic and outcome [15,16,17]. A significant minority of patients have co-existing chronic health and social problems which follow, precede, or are independent of the addictive disorder, and add complexity to clinical management [18,19,20]. The patient's family relationships and social networks may also support or hinder response [21]. These factors are screened early in treatment.

EXPO's tailored psychosocial intervention (PSI) is founded on the evidence that there are different reasons for non-response and that there will be no single best clinical intervention. The goal is to help the patient reduce the symptoms of heroin and cocaine addiction, to manage or attenuate concurrent health and social problems, to enhance engagement and to develop personal strengths and resources for recovery. The PSI has been successfully evaluated in a completed randomised controlled trial at the EXPO coordinating centre (ISRCTN number: 69313751) and further developed in a novel memory-focused cognitive therapy intervention (ISRCTN number: 164627831). We found the PSI to be well accepted and in the study. There was a relatively low level of loss to follow-up and all participants who withdrew from the study gave their consent for their data to be used in the analysis. There were no severe adverse events judged to be trial-related.

The PSI is guided by a cognitive case conceptualisation assessment to develop collaboratively a working hypothesis of how OUD is being maintained. A micro-formulation will be based on recent typical (and unusual) episodes of cocaine use and will include contexts, triggers, physical sensations, elaborated cognition (attention, memories, beliefs, appraisals [emotional 'hotspots']), motivation, coping strategies, actions, problematic affective and behavioural responses, post-opioid (and other drug use) evaluations and problems.

The EXPO PSI will be collaborative and flexible: trial psychologists will use a non-judgemental, collaborative counselling style (adapted from Motivational Interviewing [22]) and graphical representations and maps (adapted from node-link mapping to facilitate assessment, care planning, and progress review [23]). The PSI represents a point of departure from a traditional manual-guided psychological therapy in which there may be proscription of a sequence of specific techniques, or multi-modal therapies which combine two or more therapies. We will use a 'toolkit' approach with specific change methods from evidence-supported therapies chosen collaboratively with the patient and tested for effectiveness in the form of a rolling set of behavioural experiments.

During development, national clinical guidelines [24] and the therapist manuals for the following psychological therapies:

- cognitive behavioural coping and skills training (CBT [25]);
- behavioural reinforcement ('contingency management' using a budget of £60 in value shop vouchers with clinic attendance and recovery activities in addition to the traditional drug abstinence operant reinforcer [26];

- behavioural psychotherapy for couples to promote relationship stability and abstinence reinforcement [27],
- Social Behaviour and Network Therapy to recruit family members and others to accompany the patient to PSI sessions and support their recovery [28,29];
- 12-Step Facilitation Therapy for self-help group attendance [30,31]; and
- CBT methods for depression to help raise awareness of automatic thoughts, depressive evaluations and increase activity [32].

Each PSI intervention will include two or more of these specific change techniques, with supporting participant informational and self-monitoring materials. The PSI intervention sessions will aim to take place on a weekly basis dependent on the participant and therapists availability for the duration of the trial. If the participant withdraws from the treatment, they will not be withdrawn from the PSI therapy sessions unless they wish to withdraw from therapy also. A random 5% sample of session recordings per therapist will be independently rated using the University College London scale for rating core and generic (psychological) therapeutic skills [33].

8. Selection and Withdrawal of Participants

A medically qualified chief, principal or sub-investigator will evaluate the following inclusion and exclusion criteria:

8.1 Inclusion criteria

Inclusion criteria

1. Aged \geq 18 years (no upper age limit);
2. Current diagnosis of DSM-5 OUD via SCID-5-RV (moderate-severe at baseline for current episode);
3. Currently enrolled on Met (30mg/day or less) or sublingual Bup or Bup-NX (24mg/day or less) or Esp (18mg/day or less) and in the view of the clinician would be able to convert to XR-Bup within 7 days post randomisation;
4. Voluntarily seeking treatment and able to attend the clinic as required in the protocol;
5. Able to communicate in English to level required to accept standard care and psychosocial intervention;
6. Possession of a contactable personal mobile phone or landline telephone number and ability to nominate at least one locator individual with a verifiable address and a telephone number to assist with the arrangement of follow-up appointments;
7. Living circumstances judged to be of sufficient stability to be able to engage/adhere to the study protocol;
8. Is not pregnant (confirmed) or breast feeding and, if currently or intending to have potentially procreative intercourse, agrees to use a birth control method (either oral hormonal contraceptives, barrier [condom or diaphragm], or Nexplanon implant) for the duration of the study.

8.2 Exclusion criteria

1. Clinically significant medical condition or observed abnormalities on physical examination or laboratory investigation, including but not limited to:
 - (a) uncontrolled hypertension, significant heart disease (including angina and myocardial infarction in past 12 months), or any cardiovascular abnormality which is judged to be clinically significant;
 - (b) severe alcohol dependence/withdrawal syndrome which is judged to be clinically significant and may constitute a risk to the patient's safety;
 - (c) acute hepatitis taken as clinical jaundice on examination, or evidence of blood bilirubin level above the normal range for local reference criteria, or evidence of serum levels of aspartate aminotransferase, alanine aminotransferase levels that are more than three-times the upper limit of the normal range;
2. History of allergic or adverse reactions to Bup or the proprietary ATRIGEL delivery system for XR-Bup (Sublocade®)*;
3. Clinically significant or uncontrolled mental health problems (including but not limited to psychosis, bipolar disorder, schizoaffective disorder), or history or evidence of organic brain disease or dementia that may compromise safety or compliance with the study protocol;
4. Current (past 30 day) suicide plan or suicide attempt in past six months;
5. Current criminal justice involvement with legal proceedings, which in the opinion of a medically qualified investigator indicates a risk that the patient would fail to complete the study protocol due to re-incarceration or move away from the centre's catchment area.
6. Currently taking oral or depot naltrexone therapy or enrolment in any form of naltrexone therapy within 90 days prior to study screening;
7. Any contraindication to Bup*.

**Participant is ineligible if they have any allergic or adverse reactions or contraindication to Buprenorphine. If participant has any allergic or adverse reaction or contraindication to Met or naloxone, or excipients of Bup-NX or Esp they can be prescribed Bup within the trial.*

8.3 Selection of participants

All participants for EXPO will be recruited from specialist NHS addictions treatment programmes in community settings and already in receipt of opioid substitution therapy. Patients will consent prior to any screening procedures and will be randomised at a minimum of 24 hours post consent.

Post- randomisation treatment is summarised as follows:

Participants randomised to standard-of-care oral maintenance

Participants who are allocated to oral opioid pharmacotherapy will receive Bup/Met according to medical screening and informed by patient preference, following each site's usual screening, induction/stabilisation and maintenance dosing and medication dispensing procedure. There will be an additional requirement to attend the clinic after 2 weeks and then at least monthly to complete research measures and a urine drug screen procedure.

Met participants randomised to XR- Bup

Met participants will firstly be converted to Bup by following the sites local clinical procedure. Once stabilised on Bup, participants will require a period of at least 3 days on 8mg-24mg of Bup before they can receive the first dose of XR- Bup. The last dose of Bup is to be taken 1 day prior to the first dose of XR- Bup. Participants should receive their first injection of XR-Bup within 7 days of randomisation.

Bup participants randomised to XR- Bup

If the participant is prescribed less than 8mg of Bup there will be a minimum 3-day lead-in on 8mg Bup prior the first dose of XR-Bup. Participants who were previously prescribed 8mg or higher BUP can receive XR-Bup upon agreement of a suitable time with the participant and EXPO research team. The last dose of Bup is to be taken 1 day prior to the first dose of XR- Bup. Participants should receive their first injection of XR-Bup within 7 days of randomisation.

For all participants if during the transition period, the participant decides not to receive XR- Bup or clinical judgement deems it unsuitable to continue the participant will be withdrawn from the trial (ITT population).

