6.3 Dosing regimen

Bup (active sublingual comparator): The usual dose is 8-24mg/day (Esp usual dose 8-18mg/day). Clinical practice in NHS clinics is supervised (directly observed dosing) in a community pharmacy followed by provision of patient self-administered 'take home' doses according to clinical response (i.e. informed by negative urine drug screens [UDS]; adherence to prescription; retention in treatment).

Met (active oral comparator): The recommended dose is 60-120mg/day. Clinical practice in NHS clinics is supervised (directly observed dosing) in a community pharmacy followed by provision of patient self-administered 'take home' doses according to clinical response (i.e. informed by negative UDS; adherence to prescription; retention in treatment).

In the event patients in the Met/Bup arm fail to adhere to daily dosage regime they will need to follow standard clinical protocol for that clinic.

XR-Bup (IMP active injectable comparator): The recommended dose of Sublocade® (which will be adhered to in the EXPO trial) is a 300mg loading dose, administered monthly for the first 2 months, followed by a 100mg maintenance dose for the remaining 4 months. The scheduled dosing interval is 28 days and, in EXPO, the minimum interval between the two initial loading doses is 21 days to provide increased flexibility for the participant to ensure that the loading doses are achieved. All injections will be by the site investigator, medical practitioner, nurse, or nurse practitioner who has received training in the procedure. XR-Bup is for abdominal injection into adipose tissue only (not intramuscularly). The specific area is on the abdomen between the transpyloric and trans-tubercular planes with adequate subcutaneous tissue below the waistline and above the hip bone, which is free from any lesion, mole or other skin mark.

After the two 300mg loading doses, the aim is to maintain the patient on a 100mg monthly dose if they achieve:

- no unsanctioned use of opioids
- no clinically significant opioid withdrawal
- no distressing craving for opioids and the patient is satisfied with their current dose, and requesting the dose be maintained at this level.

As a clinical guide, the maintenance dose should be increased from 100mg to 300mg under the following conditions:

- The patient is not achieving desired treatment goals (e.g. persistent unsanctioned opioid use, opioid withdrawal symptoms or distressing cravings);

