10.1 Primary efficacy parameter

With a 1-week measurement grace period from randomisation, the primary endpoint is the count of days abstinent from all non-medical opioids between days 8-168 (weeks 2-24; 161 days), combined with up to 12 urine samples for opioids providing biological verification of 36 of the 161 days in the outcome measure. If the UDS shows positive, the 3 days prior to the UDS will be reported as a positive and override what is reported on the timeline follow-back interview.

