4.6 MISSING DATA

Primary and secondary count-based measures For the count-based measures two situations of missing are expected. Firstly, there will be those who have missing observations periodically through the study observation period but have remained in the study for these patients multiple imputation as described above will be adopted. The memory recall for the TLFB is 3 months therefore if a patient hasn't been to visits for a couple of months recall of up to 3 months is deemed reliable [4 - 6]. Where patients have gaps in their recall on the primary outcome (at most this would be 3 months) we would use the available data to impute for the patient. Sensitivity analysis will be conducted on this imputation using a best-case worst-case analysis, see section 6.9 for more details.

Secondly, there will be some cases of participants who completely drop out of the study during the observation period i.e. withdrawals or loss to follow ups. For these patients on the primary outcome and secondary count-based measures an offset (censoring) will be used to represent different exposures rather than multiple imputation.

Furthermore, some of the primary and secondary end points (TLFB) are based on self-report and UDS tests. Where data is available for self-report and UDS, if the results are inconsistent the UDS data will override the self-report, as indicated in section 5.2. Essentially where UDS is not available this does not result directly in missing data for the outcome as the self-report

will provide this data. However, the reliability of the self-report may be impacted therefore sensitivity analysis on missing UDS data will be conducted, see section 6.9 for more detail.

Continuous outcome measures

Missing observations are expected within the dataset. For missing items within an outcome measure, the published rules for completing missing data for the relevant measure will be applied. Where there are no missing data rules for the measure, if the number of missing items on an outcome is 20% or less, then the missing value for the item will be substituted by the individual's mean score for the remaining items on the scale (Bono, Ried, Kimberlin and Vogel 2007). If there are more than 20% missing items in the scale the outcome measure will not be calculated for the participant at that time point and multiple imputation methods will be used.

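### A randomised participant with no observed day in days 8-168, such as an early XR-Bup non-starter, cannot enter the SAP's offset model, so the primary analysis may fall short of its own ITT definition

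*Protocol*

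**What the plan says.** - Protocol 8.3 moves participants allocated to XR-Bup through a transition, with the injection due within 7 days of randomisation. If during that time a participant "decides not to receive XR- Bup or clinical judgement deems it unsuitable to continue the participant will be withdrawn from the trial (ITT population"). They leave the trial, not only the study drug.
- For the oral arm, Protocol 8.3 sets no transition: "There will be an additional requirement to attend the clinic after 2 weeks and then at least monthly to complete research measures". Under Protocol 6.3, if "patients in the Met/Bup arm fail to adhere to daily dosage regime they will need to follow standard clinical protocol for that clinic". Neither passage takes an oral participant out of the trial.
- Protocol 10.1 counts abstinent days "between days 8-168 (weeks 2-24; 161 days").
- SAP 3.1 defines the primary analysis as intention to treat, with every randomised participant analysed as allocated.
- SAP 4.6 has two rules for the count outcomes. Gaps in participants who stay in the study are imputed. For "participants who completely drop out of the study during the observation period i.e. withdrawals or loss to follow ups", "an offset (censoring) will be used to represent different exposures rather than multiple imputation".
- Protocol 12.2 names multiple imputation for missing data without excepting dropouts, and includes all patients in their allocated group.
- Protocol 8.5 asks for TLFB and UDS at withdrawal, and asks whether the participant will still give data. It schedules no later contact.

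**The concern.** A participant withdrawn in the transition whose data end by day 7 has no exposure in the outcome window. The SAP sends withdrawals to the offset, and an offset needs positive exposure. Such a participant would drop out of the primary model although the SAP counts them in its analysis set.

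The withdrawal rule applies to one arm of an open-label trial and is triggered after allocation is known. If those who decline XR-Bup differ from the rest, leaving them out undoes part of the randomised comparison. How to treat them would then be settled after lock, when the choice can affect the result.

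**Working it through.** **The plan's own figure.** Window length: 168 - 8 + 1 = 161 days, as stated. Data ending on or before day 7 give an exposure of 0.

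**Does the model accept zero exposure?** The model in SAP 6.6 is Poisson with a log link. With the offset of SAP 4.6 it is log(expected count) = log(exposure) + covariates, and log(0) is undefined. A Poisson fit to 304 simulated participants, 8 of them in the XR-Bup arm with zero exposure, stopped with an invalid-value error. It ran once they were removed, on 296 of 304. The likelihood says the same: with a count of 0 the contribution is minus exposure times rate, which tends to 0 as exposure does. The practical result is exclusion.

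**Does another rule bring them back?**
- SAP 4.6 imputation is limited to people who remained in the study.
- The fill-in rule for early final visits in SAP 5.2 excludes withdrawals.
- A TLFB taken at a withdrawal before day 8 (Protocol 8.5) contains no day in the window.
- The day 0-168 analysis in SAP 6.9 gives such a person at most 8 days (0 to 7), none in the outcome window, and is a sensitivity analysis.
- On best-case/worst-case, SAP 4.6 says "Sensitivity analysis will be conducted on this imputation using a best-case worst-case analysis", meaning imputed gaps. SAP 6.9 refers to any missing period but places the analysis under work done only if needed, and ties it to imputed data. Whether it reaches people handled by the offset is unclear.
- The per-protocol analysis in SAP 6.9 removes people who did not receive their allocation, so it cannot test the effect of leaving them out.
- Protocol 12.2 would impute them, but SAP 4.6 replaces that rule for dropouts. The two documents conflict.

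**Size, with no true effect.** The documents give neither a non-starter fraction f nor their abstinence rate r, so both are assumed. Others are abstinent on 0.60 of days (the baseline rate in SAP 4.1). The oral arm is fully followed and includes the same share of people who would not have started. All XR-Bup non-starters are taken to have zero days and are left out.

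Control rate = (1 - f) x 0.60 + f x r; XR-Bup rate = 0.60; ratio = 0.60 / control rate.

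| f (of 152) | control, r = 0.30 | ratio | ratio, r = 0.60 | control, r = 0.75 | ratio |
|---|---|---|---|---|---|
| 2% (about 3) | 0.594 | 1.010 | 1.000 | 0.603 | 0.995 |
| 5% (about 8) | 0.585 | 1.026 | 1.000 | 0.6075 | 0.988 |
| 10% (about 15) | 0.570 | 1.053 | 1.000 | 0.615 | 0.976 |

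If the 23% target difference is read as a ratio of 1.23, the r = 0.30 column is 0.0101/0.23 = 4% to 0.0526/0.23 = 23% of it.

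Bounds at r = 0.30, for f of 2%, 5% and 10%:
- all non-starter days used, (1 - f) x 0.60 / control: 0.990, 0.974, 0.947
- all abstinent, [(1 - f) x 0.60 + f] / control: 1.024, 1.060, 1.123

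**Size, with a ratio of 1.23 among starters and f = 5%.** The starter rate is 0.60 x 1.23 = 0.738.
- Left out: 1.23.
- Given the control rate: (0.95 x 0.738 + 0.05 x 0.60)/0.60 = 1.22.
- No abstinent day: 0.95 x 0.738/0.60 = 1.17.
- All days abstinent: (0.95 x 0.738 + 0.05)/0.60 = 1.25.

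**The case against.** The other side has several good points, and most limit the claim.

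- A reader might infer that non-starters usually leave before day 8. The documents give no frequency. SAP 4.5 lists treatment later than 7 days as a possible deviation, so a transition can run on, and anyone with TLFB data from day 8 onward has positive exposure and fits the offset. The problem concerns zero-day participants, not non-starters as a group.
- A reader might infer that only the XR-Bup arm loses people. Only the rule in Protocol 8.3 is specific to that arm. An oral participant who asks to stop (Protocol 6.6), withdraws (8.5) or never returns also has zero days. The illustration's fully followed oral arm is an assumption, and the plan itself allows 15% for attrition.
- A reader might take the ITT label in Protocol 8.3 as a sign that non-starters are meant to be excluded. It reads more naturally as agreeing with SAP 3.1. The intention is sound; what is lacking is a way to carry it out.
- The offset rule is worded for dropout during the observation period. If that means days 8-168, someone gone by day 7 falls outside it. The SAP then has no rule for them instead of one that fails, and they are still left out.
- The number is probably small. Protocol 8.1 requires the clinician to think conversion within 7 days possible, and at 2% non-starters the illustrated shift is about 1% or less.
- Data completeness by arm is already planned (SAP 6.5), and a plain reading of the best-case/worst-case text could cover withdrawals. That supports a short clarification but does not make the text clear.

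None of this puts a zero-day participant into the primary model.

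**Conclusion.** The point holds in limited form. For a randomised participant with no observed day in days 8-168, the SAP has no workable primary-analysis rule. Followed as written, it leaves that person out, contrary to SAP 3.1 and Protocol 12.2. Protocol 8.3 can create such participants in the XR-Bup arm through a rule the oral arm lacks, so the loss may differ by arm. It is not certain to fall on one arm alone.

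Number, size and direction are unknown. Under no true effect and the stated assumptions, the ratio runs from 0.98 to 1.05. It does not move if non-starters resemble the others, favours XR-Bup if they are abstinent less often, and goes against it if more often. A reader might conclude that the primary result is biased towards XR-Bup; the documents do not support a direction. The effect is likely modest, but the analysis would not be the one promised, and the repair is cheap. It should be fixed before lock.

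**What to change.** 1. In SAP 4.6, before lock: reconcile the dropout rule with Protocol 12.2. Include zero-day participants from either arm in the ITT analysis by multiple imputation that does not draw on XR-Bup starters alone.
2. In SAP 6.9: make the best-case/worst-case analysis unconditional and apply it to everyone randomised, including withdrawals handled by the offset and those with zero days. Align SAP 4.6 with this.
3. In SAP 6.5: add the number with zero days in the window, by arm, to the completeness tables. SAP 6.4 splits withdrawals by site only.
4. Reconcile Protocol 8.3 with 8.5 so that not starting XR-Bup ends study medication but not TLFB/UDS collection, unless consent for data is withdrawn. This would cover participants still in follow-up and within the limit in SAP 4.6, where "recall of up to 3 months is deemed reliable". No treatment decision changes.

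Items 1 to 3 are SAP wording and apply to everyone; lock is planned for about June/July 2022. Item 4 needs an amendment with ethics and regulatory approval (Protocol 17). With last recruitment at about October 2021, it helps only recently randomised participants. For them, two TLFB contacts would span the window: at week 12 for days 8-84 (84 - 8 + 1 = 77 days) and at week 24 for days 85-168 (168 - 85 + 1 = 84 days). The price is a possibly wider range or a less favourable estimate.
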